- a. Baseline testing must be started within seven (7) days of eligibility confirmation. Baseline Visit date is defined as the start date of all Baseline testing. All Baseline testing must be completed within thirty (30) days of the Baseline Visit date, with the following exceptions:
  - If the Baseline Visit date is within 3 months of the Registry/Screening Visit testing date for the visual acuity (VA), static perimetry, SD-OCT (volume and V/H), ophthalmic exam or IOP exams, the testing performed as part of the Registry/Screening Visit may be used for the Baseline Visit. ***A second static perimetry test would still need to be performed at the Baseline Visit, as noted in h below.***
  - PROs may be completed in person or remotely any time within 6 months after Baseline Visit date.
- b. All NHS Follow-up Visit testing must be completed on the same day, with the following exception:
  - PROs may be completed in person or remotely any time within the Allowable Window of the associated visit.
- c. Ophthalmic exam includes slit-lamp biomicroscopy and indirect ophthalmoscopy. It is recommended that the ocular exam be completed at approximately the same time of day at each visit using the same equipment.
- d. Intraocular pressure (IOP) measurements are to be taken prior to pupil dilation.
- e. Axial length and corneal curvature measurements will be completed at the Baseline Visit for all participants. Only individuals who are under 18 years old at the Baseline Visit will continue to have measurements taken at every annual visit until study completion.
- f. If ERG has been undetectable in the past, there is no need to perform at Baseline Visit; if ERG is undetectable at Baseline Visit, there is no need to perform at 48M - at the investigator's discretion.

- g. For static perimetry and microperimetry, all participants will complete two tests for the Baseline Visit. The results will be compared according to the visual field criteria in section 4.3.2 to determine if a third test is needed.
- h. If a site does not have the required equipment, participation in this test may be waived **with approval from the Coordinating Center**.

## SCHEDULE OF STUDY VISITS AND PROCEDURES FOR THE NATURAL HISTORY STUDY: VISION COHORT 3

Visit	Baseline a	12M	24M	36M	48M b
Target Windows	(Day 0)	Wk 52 ± 4 (Phone call only)	Wk 104 ± 4 (Phone call only)	Wk 156 ± 4 (Phone call only)	Wk 208 ± 4
Participant-Level Procedures					

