- 679       13. Full-field Stimulus Threshold (FST)\*
- 680       14. Static Perimetry (SP)
- 681           ♦ Two (2) tests will be performed. The clinical site will compare the certified  
682           technician determined mean sensitivity from test one (1) versus test two (2).
- 683               **(a)** If the absolute value of the difference between the two tests is  $\leq 2.4$  dB,  
684               then the participant passes static perimetry reliability criteria. A third test  
685               is not needed.
- 686               **(b)** If the absolute value of the difference between the two tests is  $> 2.4$  dB,  
687               then the participant does not pass static perimetry reliability criteria. A  
688               third test will be required.
- 689           ♦ ***If the Baseline Visit date is within 3 months of the Registry/Screening Visit***  
690           ***testing date – the SP performed during the Registry/Screening Visit may be***  
691           ***considered the first test and does not need to be repeated. Only the second test***  
692           ***will need to be performed at the Baseline Visit; the need for a third test will be***  
693           ***assessed using Test 1 from the Registry/Screening Visit and Test 2 from the***  
694           ***Baseline Visit.***
- 695       15. Fundus Guided Microperimetry (MP)\*
- 696           ♦ Two (2) tests will be performed. The clinical site will compare the certified  
697           technician determined mean sensitivity from test one (1) versus test two (2).
- 698               **(a)** If the absolute value of the difference between the two tests divided by  
699               the average between them is  $\leq 50\%$  OR the absolute value of the  
700               difference between the two tests is  $\leq 0.5$  dB, then the participant passes  
701               the microperimetry reliability criteria. A third test is not needed.

702  
 703 (b) If the absolute value of the difference between the two tests divided by  
 704 the average between them is > 50% AND the absolute value of the  
 705 difference between the two tests is > 0.5 dB, then the participant does not  
 706 pass microperimetry reliability criteria. A third test will be required.

707 *\*If a site does not have the required equipment, participation in this test may be waived **with***  
 708 ***approval from the Coordinating Center.***

709 **4.3.3 Vision Cohort 3**

- 710 1. Medical updates to include

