1324 **NHS Objective 2 (Structure-Function Relationship)**

- 1325 ➤ **NHS Objective 2** is to explore whether structural outcome measures can be validated as  
 1326 surrogates for functional outcomes in individuals with disease-causing genetic variants,  
 1327 **within gene** (*where sample size 20 or more*).
- 1328 ○ **Analysis plan:** Scatterplots and Spearman correlation coefficients of changes in  
 1329 functional and structural outcome measures of progression from baseline to each  
 1330 visit will be evaluated.

1331 **NHS Objective 3 (Risk Factors for Progression)**

- 1332 ➤ **NHS Objective 3** is to explore possible risk factors (genotype, phenotype,  
 1333 environmental, and comorbidities) for progression of the outcome measures at 4 years in  
 1334 individuals with disease-causing genetic variants, **within-gene** (*where sample size 40 or*  
 1335 *more*).
- 1336 ○ **Analysis plan:** The distribution of each outcome in terms of both absolute  
 1337 change and percent change from baseline to 4 years will be summarized  
 1338 (including tabulating categorically, as well as means, standard deviations,

1339 medians, quartiles), stratified by categorical levels of each potential risk factor  
 1340 of interest (listed below). Potential risk factors to evaluate include:

- 1341 ○ Phenotypic:
  - 1342 ■ Clinical diagnosis (if applicable)
  - 1343 ■ Duration of disease
  - 1344 ■ Age of onset of initial vision symptoms
  - 1345 ■ Gender
  - 1346 ■ Race/ethnicity
  - 1347 ■ Visual Acuity
  - 1348 ■ Lens Status (phakic/pseudophakic/aphakic)
- 1349 ○ Genotypic:
  - 1350 ■ Characterizations of the variants
- 1351 ○ Environmental factors
  - 1352 ■ Smoking status at baseline
  - 1353 ■ Vitamin A use at baseline
  - 1354 ■ Docosahexaenoic acid (DHA) use at baseline
  - 1355 ■ Lutein use at baseline

1356 **Other Planned Analyses**

- 1357 ➤ Analysis plan for variability of repeat perimetry testing at baseline: Scatterplots and  
 1358 Spearman correlation coefficients for pairs (first versus second) of testing values for each  
 1359 repeated perimetry test. Bland-Altman plots of difference versus the mean value will be  
 1360 inspected. The intraclass correlation coefficient of the values and the within-eye variance will  
 1361 be estimated.
- 1362 ➤ Analysis plan for the symmetry of left eye versus right eye: At baseline and each subsequent  
 1363 testing time, the symmetry of the test result values from the left and right eyes will be  

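### The static perimetry repeatability analysis pools pairs that may be same-day with pairs taken at two visits up to about 3 to 4 months apart, so its within-eye variance is a mixture

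*Protocol*

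**What the plan says.** Three rules in the protocol meet here.

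- **The analysis.** Section 9.2.2, Other Planned Analyses, takes "Spearman correlation coefficients for pairs (first versus second) of testing values for each" repeated perimetry test. Bland-Altman plots are to be "inspected. The intraclass correlation coefficient of the values and the within-eye variance will" be estimated. The interval between the two tests is not mentioned.
- **The test pairs.** Section 4.3.2, item 14 (Vision Cohorts 1 and 2): "Two (2) tests will be performed. The clinical site will compare the certified" technician's mean sensitivity from one against the other. If Baseline is within 3 months of Registry testing, "the SP performed during the Registry/Screening Visit may be" counted as the first test. The need for a third test is then "assessed using Test 1 from the Registry/Screening Visit and Test 2 from the" Baseline Visit. Footnote a of the schedule for Vision Cohorts 1 and 2 says the same: "If the Baseline Visit date is within 3 months of the Registry/Screening Visit testing date for the visual acuity (VA), static perimetry" and other listed tests may be carried over, but "A second static perimetry test would still need to be performed at the Baseline Visit".
- **The Baseline window.** The same footnote states: "All Baseline testing must be completed within thirty (30) days of the Baseline Visit date". Two Baseline tests may therefore fall on one day or on different days.

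Microperimetry is also done twice at Baseline, but it is not a Registry test and has no carry-over rule.

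**The concern.** A within-eye variance from paired tests is useful only if one knows what varied between them. Two tests in one session share the same day, setup and patient state, so their difference is mostly test noise. Two tests at separate visits add session-to-session variation and any true change in the interval. Section 9.2.2 asks for one set of estimates over both kinds.

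This matters because section 1.1.2 lists reproducibility, and how far within-person change exceeds measurement variability, among the properties needed to choose an endpoint, and says they should be understood within each gene. Change between annual visits always contains between-visit variation. A variance drawn mostly from same-day pairs would understate the relevant noise. One drawn mostly from Registry-Baseline pairs would come closer to it. A pooled figure of unknown mix cannot be assigned to either use.

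**Working it through.** **1. Possible gaps between the two tests.**
- Both tests at Baseline: 0 to 30 days (the 30-day window).
- Registry test reused, second test on the Baseline Visit date: up to about 3 months (about 91 days).
- Registry test reused, second test at the end of the window: 91 + 30 = 121 days, about 4 months.

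A reused pair always spans two visits. A pair without reuse may be same-day but need not be.

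**2. What decides the mix.** Under section 3.1, a participant whose gene is already a target gene at genetic confirmation is asked back for Baseline. The Protocol Outline gives about 30 days for genetic screening, so reuse is feasible. If the gene is not yet designated, the participant waits in the Registry, for up to 48 months according to the Outline. Once more than 3 months have passed since Registry testing, reuse is not allowed. Where it is allowed, the site may still do both tests at Baseline. The share of reused pairs thus follows from designation timing, screening date, confirmation time and site choice, and can differ by gene.

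**3. What a pair estimates.** Let sw² be the same-session test variance, sb² the between-session variance, and μ and τ the mean and SD of true change over the gap. With d the difference between the two tests:
- same-session pair: E[d²]/2 = sw²
- between-visit pair: E[d²]/2 = sw² + sb² + (μ² + τ²)/2
- pooled, with share p of between-visit pairs: sw² + p × [sb² + (μ² + τ²)/2]

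The pooled value moves with p even when the test behaves identically in every gene.

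**4. How much the documents can size.** The protocol gives no value for sw, sb or p, and no planned figure to reproduce. The only component it informs is progression. The sample size example in section 9.1.3 quotes a 24-month change in static perimetry hill of vision of -12.4% (SD 28.2%) from the reference study. Scaled linearly:
- 3 months: -12.4 × 3/24 = -1.55%, or 27.8 × 0.0155 = 0.43 dB-sr on the reference baseline mean of 27.8 dB-sr (section 9.1.2)
- 4 months: -12.4 × 4/24 = -2.07%

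At 3 months, mean change adds μ²/2 = 1.55²/2 = 1.20 (in squared percentage points). Against an assumed sw of 10%, that is 1.20/100 = 1.2% of the same-session variance; for sw of 5% it is 1.20/25 = 4.8%. Differences between eyes in true change (τ) would add more, but the quoted SD of 28.2% also contains measurement noise, so τ cannot be separated from it. The between-session term sb² is unknown.

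**The case against.** The strongest reply is that this is detail for a statistical analysis plan. The analysis is descriptive, sits outside the numbered objectives, and can be split later because test dates exist. It can be added that reused pairs pull the estimate towards the between-visit variability that matters for annual change, and that splitting thins samples that are already small within gene.

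Much of this stands, and it limits the weight of the point. It does not remove it: the protocol itself creates the two kinds of pair and itself specifies a first-versus-second analysis across them, so the mixture follows from stated rules. The pull towards between-visit variability helps only if the mix is known.

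A reader might infer more than the documents support:
- **That genes designated late have no reused pairs.** Designation is ongoing (section 4.1), and nothing closes Registry enrollment in a gene once it is designated. A late-designated gene can include people screened shortly before or after designation. Nor does early designation guarantee reuse, which is optional.
- **That limits of agreement widen by a particular percentage.** Any such figure only restates an assumed ratio of between-session to same-session variance.
- **That a planned comparison is biased.** Section 9.2.2 plans no comparison of repeatability between genes, or between static perimetry and microperimetry.
- **That all Baseline pairs are same-visit.** They may be up to 30 days apart.

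**Conclusion.** The point holds as a modest one. As written, the static perimetry intraclass correlation, Bland-Altman agreement and within-eye variance come from a mixture of pairs that may be same-day and pairs up to about 3 months apart, or about 4 months at the limit. The mix is set by circumstances unrelated to the test and can differ between genes. The direction is clear: between-visit pairs can only add expected variance. The size is not derivable. Mean progression contributes little at 3 months, assuming linear change and that the reference study's rate carries over to other genes. A material effect would need appreciable session-to-session variation or wide differences in true change. Only a secondary analysis is affected, and only for static perimetry does the Registry carry-over arise.

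**What to change.** In section 9.2.2 or the statistical analysis plan, use recorded test dates to report static perimetry repeatability separately for same-day pairs and different-day pairs, the latter including Registry-Baseline pairs. Give the number of pairs and the distribution of intervals in each group. Where a gene is too small to split, model the squared difference on the interval, or at least show the mix beside the pooled estimate. State that the between-visit estimate is the one to use when judging change between annual visits.

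A split at same-day versus different-day is preferable to Baseline-only versus reused, because a Baseline-only group would still mix same-day pairs with pairs weeks apart.

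No visit, test or data item is added. The cost is fewer pairs per estimate: a gene with 20 participants offers at most 20 pairs per eye before any split, so the separate estimates will be imprecise in small genes.

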## Chapter 10: Data Collection and Monitoring

### 1378 10.1 Case Report Forms and Other Data Collection

1379 The main study data are collected on electronic case report forms (eCRFs). When data are  
 1380 directly collected in electronic case report forms, this will be considered the source data. For any  
 1381 data points for which the eCRF is not considered source (e.g., lab results that are transcribed  
 1382 from a printed report into the eCRF), the original source documentation must be maintained in  
 1383 the participant's study chart or medical record. **This source must be readily verifiable against**  
 1384 **the values entered into eCRF.** Even where all study data are directly entered into the eCRFs at  
 1385 office visits, evidence of interaction with a live subject must be recorded (e.g., office note, visit  
 1386 record, etc.) and provided to the coordinating center for review.

1387 Each participating site will maintain appropriate medical and research records for this trial, in  
 1388 compliance with International Council for Harmonisation of Technical Requirements for  
 1389 Pharmaceuticals for Human Use (ICH) E6 and regulatory and institutional requirements for the  
 1390 protection of confidentiality of participants

#### 1391 10.1.1 Central Genetics Auditor (CGA)

1392 The CGA will review the genetic lab report(s) submitted by the clinical site during genetic  
 1393 screening and will document their verification of these genetic data on the FFB Consortium  
 1394 study website.

#### 1395 10.1.2 Genetics Committee (GC)

1396 In addition to providing assistance in the interpretation/evaluation of whether the mutations are  
 1397 causative of the disease on the FFB Consortium study website, the Genetics Committee will  
 1398 review and provide approval for the use of genetic reports from research labs to be used for  
 1399 determining participant eligibility.

#### 1400 10.1.3 Reading Center (RC)

1401 Reading Centers will conduct grading of the study data collected using the FFB Consortium  
 1402 study website. The Reading Centers will provide the graded data through a data transfer or by  
 1403 entering the graded data on the study website. These data will remain in the study database and  
 1404 will not be provided to the clinical site.

### 1405 10.2 Study Records Retention

1406 Each participating site will maintain appropriate medical and research records for this trial, in  
 1407 compliance with ICH E6 and regulatory and institutional requirements for the protection of  
 1408 confidentiality of participants.

1409 Study documents will be retained for a minimum of six (6) years from the date on which the CC  
 1410 receives IRB approval to close the study. These documents should be retained for a longer  
 1411 period, however, if required by local regulations. No records will be destroyed without the  
 1412 written consent of the Sponsor. It is the responsibility of the Sponsor to inform the Principal  
 1413 Investigator (PI) when these documents no longer need to be retained.

1414 **10.3 Quality Assurance and Monitoring**

1415 Designated personnel from the Coordinating Center will be responsible for maintaining quality  
 1416 assurance (QA) and quality control (QC) systems to ensure that the clinical portion of the trial is  
 1417 conducted and data are generated, documented and reported in compliance with the protocol,  
 1418 Good Clinical Practice (GCP) and the applicable regulatory requirements, as well as to ensure  
 1419 that the rights and wellbeing of trial participants are protected and that the reported trial data are  
 1420 accurate, complete, and verifiable.

1421 A risk-based monitoring (RBM) plan will be developed and revised as needed during the study,  
 1422 consistent with the FDA “Guidance for Industry Oversight of Clinical Investigations — A Risk-  
 1423 Based Approach to Monitoring” (August 2013). Study conduct and monitoring will conform  
 1424 with 21 Code of Federal Regulations (CFR) 312. This plan describes in detail who will conduct  
 1425 the monitoring, at what frequency monitoring will be done, at what level of detail monitoring  
 1426 will be performed, and the distribution of monitoring reports.

1427 The data of most importance for monitoring at the site are participant eligibility and adverse  
 1428 events. Therefore, the RBM plan will focus on these areas. As much as possible, remote  
 1429 monitoring will be performed in real-time with on-site monitoring performed to evaluate the  
 1430 verity and completeness of the key site data. Elements of the RBM may include:

- 1431 ♦ Qualification assessment, training, and certification for sites and site personnel
- 1432 ♦ Oversight of Institutional Review Board (IRB) coverage and informed consent  
1433 procedures
- 1434 ♦ Central (remote) data monitoring: validation of data entry, data edits/audit trail,  
1435 protocol review of entered data and edits, statistical monitoring, study closeout
- 1436 ♦ On-site monitoring (site visits): source data verification, site visit report
- 1437 ♦ Communications with site staff
- 1438 ♦ Patient retention and visit completion
- 1439 ♦ Quality control reports
- 1440 ♦ Management of noncompliance
- 1441 ♦ Documenting monitoring activities
- 1442 ♦ Adverse event reporting and monitoring

1443 Coordinating Center representatives or their designees may visit the study facilities at any time in  
 1444 order to maintain current and personal knowledge of the study through review of records,  
 1445 comparison with source documents, observation and discussion of the conduct and progress of  
 1446 the study. The investigational site will provide direct access to all trial-related sites, source  
 1447 data/documents, and reports for the purpose of monitoring and auditing by the Sponsor, and  
 1448 inspection by local and regulatory authorities.

1449 **10.4 Protocol Deviations**

1450 A protocol deviation is any noncompliance with the clinical trial protocol, GCP, or procedure  
 1451 requirements. The noncompliance may be either on the part of the participant, the Investigator(s),  
 1452 or the study site staff.

1453 A significant (or major) deviation is any deviation that departs from the established materials in  
1454 such a way that it poses an increase in the risk to the study participants, adversely affects the  
1455 welfare, rights, or safety of the research study participants, or negatively influences the scientific  
1456 study integrity. As a result of significant deviations, corrective and preventive actions are to be  
1457 developed by the site and implemented promptly.

1458 The site Principal Investigator (PI) and study staff are responsible for knowing and adhering to  
1459 their IRB/EC requirements.

1460

## **Chapter 11: Ethics/Protection of Human Participants**

1461

### **11.1 Ethical Standard**

1462

The Principal Investigator (PI) will ensure that this study is conducted in full conformity with

1463

Regulations for the Protection of Human Participants of Research in accordance with ICF

1464

E6/GCP, EC requirements, and local laws and regulations, as applicable.

1465

### **11.2 Institutional Review Boards**

1466

The protocol, informed consent form(s), recruitment materials, and all participant materials will

1467

be submitted to the IRB for review and approval. Approval of both the protocol and the consent

1468

form must be obtained before any participant is enrolled. Any amendment to the protocol will

1469

require review and approval by the IRB before the changes are implemented to the study. All

1470

changes to the consent form will be IRB approved; a determination will be made regarding

1471

whether previously consented participants need to be re-consented.

1472

### **11.3 Informed Consent Process**

1473

#### **11.3.1 Consent Procedures and Documentation**

1474

Informed consent is a process that is initiated prior to the individual's agreeing to participate in

1475

the study and continues throughout the individual's study participation. Extensive discussion of

1476

risks and possible benefits of participation will be provided to the participants and their families.

1477

Consent forms will be IRB/EC-approved, and the participant will be asked to read and review the

1478

document. The Investigator(s) will explain the research study to the participant and answer any

1479

questions that may arise. All participants will receive a verbal explanation in terms suited to their

1480

comprehension of the purposes, procedures, and potential risks of the study and of their rights as

1481

research participants. Participants will have the opportunity to carefully review the written

1482

consent form and ask questions prior to signing.

1483

The participants will have the opportunity to discuss the study with their surrogates or think

1484

about it prior to agreeing to participate. The participant will sign the informed consent document

1485

prior to any procedures being done specifically for the study. The participants may withdraw

1486

consent at any time throughout the course of the trial. A copy of the informed consent document

1487

will be given to the participants for their records. The rights and welfare of the participants will

1488

be protected by emphasizing to them that the quality of their medical care will not be adversely

1489

affected if they decline to participate in this study.

1490

